### Objective 2 specific methods:

Evaluate the efficacy of HITSytem 2.1 to increase viral suppression (<1,000 ml/copies) through 6 months postpartum, per Kenyan national guidelines

To understand the efficacy of HITSytem 2.1 to increase viral suppression we will systematically measure VL of all women (intervention and control) at the time of delivery and by 6 months postpartum for those missing a repeat postpartum VL to approximate maternal VL during the antenatal and early postnatal periods.

**Tracking Viral Load.** The HITSytem 2.1 intervention's impact on maternal viral suppression rates will be assessed through VL tests at delivery and at each woman's first routine postpartum VL test. VL testing at delivery goes beyond the guidelines and is done solely for research purposes. To ensure that this testing does not interfere with our ability to examine routine VL testing postpartum and avoid confusion regarding VL guidelines, maternal VL testing at delivery (within 4 weeks of delivery) will be coordinated by study staff, processed by a qualified research laboratory (not the clinical laboratory) and results maintained outside of clinic files. This additional VL test for research purposes only will be described to study candidates during informed consent. Results of the first routine postpartum VL test will be collected from the medical record. Per guidelines, the first postpartum VL test should occur within 6 months, so even women tested very late in pregnancy will be due for retesting by 6 months postpartum. Participants without a repeat VL test by 6 months postpartum will be tracked by study staff through phone or in-person contact to schedule a VL test within a 4-week window, i.e. before 7 months postpartum.

Figure 1. Viral load testing schedule to assess maternal viral suppression

**Participant tracking for VL among participants 'lost to follow-up' (LTFU).** Measurement of viral suppression rates in either study arm can be skewed if detectable VL is more/less frequent in LTFU patients. Therefore, we will use a weighted sampling-based approach to track patients who receive no delivery VL test or postpartum VL test within 6 months. From a twice monthly LTFU patient list for each site, participants will be targeted for active tracking including phone calls and home visit to reach women who disengaged from care prior to or by the time of delivery, and thus had no VL sample collected at the time of delivery. Study staff conducting home visits (mentor mother and community health worker) will be thoroughly trained on protection of confidentiality, especially when participants are not home or have relocated. Visits will be introduced as well-baby visits to protect confidentiality, and a dried blood spot sample (DBS) for VL will only be collected once privacy is confirmed and consent provided. Visits will be rescheduled if privacy is perceived to be compromised at any time. Women whose infant has not yet tested for HIV will be offered sample collection for infant testing, and DBS will be transported for processing (Appendix 2F, Home Visit Survey).

**Objective 2 Outcomes.** The primary outcome for Objective 2 is the proportion of clients with a detectable VL at delivery and within 6 months postpartum. Given the ongoing shortage of VL testing in the country, all women who have not received a postpartum VL test by 6m postpartum will be offered a "study-initiated" VL test. These samples will be collected and shipped in the same manner as the delivery VL test and will be supported by study funds and sent to the KEMRI CDC lab for processing. Furthermore, at the 6m visit, infants will be offered an HIV PCR test, which will also be sent to KEMRI CDC lab. Participants who receive these "study-initiated" tests will not be considered "completely retained" for the aim 1 primary outcome; however, these data are necessary for the aim 2 outcome. Secondary outcomes associated with Objective 2 will include VL test coverage (proportion with VL test in antenatal and postpartum periods, per guidelines), VL

test efficiency (turn-around time from sample to result, and turn-around time from result to patient notification), VL test utility (proportion of detectable VL results with clinical action per guidelines, such as: intensified adherence counseling and/or ARV regimen change), and repeated VL testing among those with detectable VL. We will document outcomes for pregnant and breastfeeding women who are LTFU to better enumerate outcomes for this population.

**Statistical analyses for Objective 2.** We will test for differences on binary outcomes between arms using logistic mixed models with adjustment for clustering and select covariates. After transformation (e.g., log) of turn-around time values if needed, differences in time will be assessed using appropriate generalized or linear mixed models. Post hoc analyses will assess person-level characteristics as moderators of the HITSystem 2.1 effect to assess whether the HITSystem 2.1 is more effective for specific subgroups. Any differences will guide future adaptations to improve efficacy among specific populations. The same methods described for mediation analysis of information and motivation will be applied in Objective 2.

Objective 3 specific methods:

**Evaluate the reach, effectiveness, adoption, implementation fidelity and maintenance (REAIM model) of HITSystem 2.1 using system data and surveys with providers and patients.**

We will evaluate the implementation of HITSystem 2.1 components to guide programmatic implementation and increase sustainable use in government health facilities. The RE-AIM framework is well suited to evaluate the implementation of system-level interventions, and outlines the public health impact as the intersection between: Reach, Effectiveness, Adoption, Implementation, and Maintenance, Table 6.

**Reach:** We will assess the proportion of eligible participants enrolled in HITSystem 2.1 at intervention sites by comparing HITSystem 2.1 enrollment with paper-based PMTCT registers. Reasons for non-participation will be documented for all eligible participants not included in the study. Among participants, data collected through the patient enrollment surveys will be used to describe characteristics of the sample and compared with national estimates to assess representativeness to national population of HIV+ pregnant women.

**Effectiveness:** Objectives 1 & 2 assessing complete PMTCT retention and viral suppression will evaluate effectiveness. We will also measure adverse outcomes as a result of the program.

**Adoption:** At the *facility-level*, we will note any facilities which decline study participation and reasons for refusal. Among participating hospitals, the facility assessment form – filled out pre-mid-post study implementation – will collect data regarding resource level, patient-provider ratios, annual volume, implementing partners and outside support, and other facility details will be used to assess representativeness with Kenyan health care facilities. At the *provider-level*, adoption will be evaluated through provider surveys, assess the degree to which providers used HITSystem 2.1, determine which components were most beneficial, and assess facilitators and barriers to HITSystem 2.1 adoption. *Patient surveys* will similarly assess utility of SMS outreach components and suggestions to optimize benefit.

**Implementation:** Any changes to HITSystem 2.1 programming or study protocols will documented in research logs and/or through IRB amendments. Any changes to HITSystem 2.1 implementation at the hospital-level (i.e. location changes of desktop to better suit workflow, changes in key users, etc) will also be documented in study logs to guide implementation recommendations. We will review all HITSystem texting logs during the implementation period to assess fidelity of the SMS component by calculating the proportion of SMS sent according to participant preference (correct frequency and content) and the proportion received by a functioning mobile number. We will compare this with participants' reports of the number of SMS received as part of the study and the reasons for these SMS, which will be collected as part of the patient surveys.

**Maintenance:** Continued HITSystem 2.1 enrollment after the study enrollment period has ended (years 3-5) and utilization after the study follow up period (year 4-5) will serve as an indicator of system maintenance. In Years 3-5, the US-based study manager will compare the overall number of HITSystem 2.1 enrolments with PMTCT registers to assess if reach is being maintained. Using the HITSystem 2.1-generated alerts report, s/he will document the number and duration of provider alerts as a measure of system use.

**Statistical analyses for Objective 3:** Survey data will be summarized using descriptive statistics to calculate proportions, medians, and mean values. The content of field notes (documentation of contextual events over the course of the study

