Maternal viral load (VL) levels provide a clear benchmark to guide clinical management and minimize risk of mother-to-child transmission. Limited evidence suggests that mothers with suppressed VL have very low risk of transmitting the virus to their infant. During *pregnancy*, estimates of the risk of mother-to-child transmission range from 0% to 5% when maternal VL is <1,000 copies/mL and 8.5%-37% when maternal VL is >1,000 copies/mL—with higher VL associated with greater risk of transmission. During *breastfeeding*, rates of mother-to-child transmission among mothers on ART range from 0.24%-3.1%, with a pooled risk of 1.8%, and higher rates among mixed-fed infants. Among the few studies tracking maternal VL and mother-to-child transmission through breastfeeding, all transmitting mothers had at least one detectable plasma VL (>1000 copies/mL) during the follow up period, and/or a documented treatment interruption.

Clinical intervention to address high maternal VL during pregnancy or breastfeeding can include enhanced adherence support, regimen switching, and enhanced infant prophylaxis. These interventions are only feasible if: 1) eligible patients receive VL tests, 2) results are promptly returned to health facilities, and 3) detectable VL results lead to clinical action. For women already on ART when presenting for antenatal care, Kenya's PMTCT guidelines call for a VL test as soon as pregnancy is confirmed. Women newly diagnosed with HIV per routine testing during pregnancy receive their first VL test 3 months after ART initiation. Repeat testing occurs every 6 months. VL testing should, therefore, reach most women 1-2 times during pregnancy and 1-4 times during breastfeeding. National data on the uptake of these tests in PMTCT have not been published, but our pilot data of records reviewed at 4 Kenyan hospitals indicate insufficient VL testing among pregnant (49.8%) and breastfeeding (by 6 months postpartum) (21.7%) women, an average of 2.3 weeks' turnaround time to get VL test results, and few patients (36.0%) being notified of their results. Only 28.9% of patients with detectable viral loads had any documented evidence of clinical action taken. Delays in timely clinical action after detectable VL results were cited in PEPFAR's Kenya Country Operational 2017 Plan as a key barrier in Kenya, and as a target for interventions.

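### The Objective 2 analysis omits the tracing weights, a rule for combining the two viral load tests, and a method for turnaround times with no end date

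*Combined protocol and SAP*

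**What the plan says.** All of this is in the combined protocol and SAP, mainly under Objective 2 specific methods.

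- **Primary outcome** (Objective 2 Outcomes): "the proportion of clients with a detectable VL at delivery and within 6 months postpartum". Under 4.0 Objectives, the Objective 2 hypothesis also joins the two times with *and*, while Objective 4 uses *or* for pregnancy and postpartum.
- **Lost women** (Participant tracking): the plan recognises that "Measurement of viral suppression rates in either study arm can be skewed if detectable VL is more/less frequent in LTFU patients", and for that reason says "we will use a weighted sampling-based approach". The weights are not defined. The same section also says that VL will be measured in all women, and that every woman without a postpartum VL by 6 months will be offered a study-initiated test.
- **Analysis of binary outcomes** (under Statistical analyses for Objective 2), in the plan's words: "We will test for differences on binary outcomes between arms using logistic mixed models with adjustment for clustering and select covariates". No weights, missing-VL rule or sensitivity analysis follow.
- **Turnaround** (secondary outcomes): there are two, "turn-around time from sample to result, and turn-around time from result to patient notification". After transformation if needed, "differences in time will be assessed using appropriate generalized or linear mixed models". Nothing is said about results that never come back or are never passed on. In the pilot record review, section 1 reports "few patients (36.0%) being notified of their results".

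**The concern.** Three gaps sit in one short analysis paragraph.

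1. **Weights.** The planning rates of 35% and 11% are averages over retained and lost women. If only some lost women are reached and the model is unweighted, each traced woman counts once and does not stand for those not reached. The model then targets a different quantity from the one the sample size was built on.
2. **Combining rule.** Both visits detectable, either visit detectable, two separate endpoints and repeated measures are four different outcomes. Under the first two, a woman with one VL may have no definable value. Such women may be common: the sample-size section reports 198 women who missed routine testing in the reagent stockout. This is a primary outcome with an interim test for superiority, so a rule chosen after seeing data would weaken control of the overall 0.05 level.
3. **Turnaround.** A mixed model on times needs an end date, so results never returned or never notified drop out by default. HITSystem 2.1 alerts providers to results not posted and mothers not informed. An analysis of completed intervals therefore conditions on something the intervention is meant to change.

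**Working it through.** **Inputs from the plan** (Sample size considerations for Objective 2; Table 5). Detectable VL among women tested is 31.3% in control and 9.1% in intervention. Women lost have at least 1.5 times the risk. Loss by delivery is 24% in the control site. There are 6 clusters per arm, with the interim at 67% of 75, about 50 per cluster, and alpha .025. The ICC of .05 is stated for Objective 1 and assumed here; a two-sided test is also assumed.

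**Reproducing the plan's figures.** 31.3% × (0.76 + 1.5 × 0.24) = 31.3% × 1.12 = 35.1%, and 9.1% × 1.12 = 10.2%. These match the stated 35% and 10.2% (rounded up to 11%). The effective interim n per arm is 300 / (1 + 49 × 0.05) = 300 / 3.45 = 87. Power is then 94.3% (pooled z) or 95.4% (unpooled z) for .35 vs .11, against 95% stated. For .30 vs .11 it is 81.2% or 82.9%, against 83% stated.

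**(a) Weights.** Let p be the risk if retained, L the fraction lost and s the fraction of lost women traced.

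- All women: p[(1−L) + 1.5L]
- Unweighted: p[(1−L) + 1.5Ls] / [(1−L) + Ls]

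Assumptions outside the plan: intervention loss of 10%, and s of one quarter to one half.

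| | Control (L = 24%) | Intervention (L = 10%) | Difference |
|---|---|---|---|
| All women | 31.3% × 1.12 = 35.1% | 9.1% × 1.05 = 9.6% | 25.5 points |
| Half traced | 31.3% × 0.94/0.88 = 33.4% | 9.1% × 0.975/0.95 = 9.3% | 24.1 points |
| Quarter traced | 31.3% × 0.85/0.82 = 32.4% | 9.1% × 0.9375/0.925 = 9.2% | 23.2 points |

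The loss is 1.4 to 2.3 points, about 6% to 9% of the difference. With the plan's 24% lost in both arms, the all-women difference is 24.9 points. Unweighted, it is 23.7 with half traced, 23.0 with a quarter and 22.2 with none. If every lost woman is reached, the two quantities agree.

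**(b) Combining rule.** Read 35% and 11% as rates at each visit (assumption), with between-visit correlation φ (assumption). P(both) = p² + φp(1−p), and P(either) = 2p − P(both).

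| φ | Both visits | Difference | Either visit | Difference |
|---|---|---|---|---|
| 0 | 12.3% vs 1.2% | 11.0 points | 57.8% vs 20.8% | 37.0 points |
| 0.7 | 28.2% vs 8.1% | 20.1 points | 41.8% vs 13.9% | 27.9 points |

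Interim power by the pooled-z method above is about 75% (both) or 99.9% (either) at φ = 0, and about 87% or 98% at φ = 0.6.

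**(c) Turnaround.** 100% − 36.0% = 64.0% of patients in the pilot review had no recorded notification, hence no result-to-notification time. Sample-to-result time is missing only where no result came back.

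**The case against.** The strongest reply is that the plan is silent and not wrong. A reader might infer that it excludes untested women, or denies traced women any weight. It says neither: weighting is announced in the tracking paragraph and simply not repeated in the analysis paragraph. That stands, and the point is that the weights are not carried through.

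The section also pursues every woman without a VL. If that is what happens, tracing is not a sample and there is nothing to weight up by design. This stands too, but it moves the problem to non-response.

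A reader might infer that an unweighted model would lose most of the effect. Such a result needs, for example, a 25% retained risk in both arms and a doubled risk if lost: with the same loss and tracing fractions, 3.5 points then falls to 2.1 or 1.2. The plan's 31.3% vs 9.1% among women in care contradicts equal retained risk.

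The 35% and 11% derive from women with at least one VL result, so they are closer to per-woman than per-visit rates. The ranges in (b) show how far the definition can move the result; they do not predict it.

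A reader might also infer that 64% of turnaround times will be lost, mostly in control. The documents do not support this. The 36.0% comes from a pre-trial review at 4 hospitals, with no stated denominator and no arm comparison, and non-notification touches only one of two secondary outcomes. Any figure for the distortion would need an intervention notification rate that the documents do not give.

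**Conclusion.** The concern holds as a set of specified omissions of unequal weight. The missing combining rule is the most serious. It leaves a primary outcome open to readings whose arm differences run from 11 to 37 points under the stated assumptions (35% vs 11% per visit, correlation 0 to 0.7). The absent weights cause a modest dilution on the plan's own risks: 23.2 to 24.1 points against 25.5, given assumed loss of 24% vs 10% and a quarter to half of lost women traced. The dilution vanishes if all are reached. The turnaround gap concerns secondary outcomes and cannot be sized from the documents; the pilot's 36.0% only illustrates how many result-to-notification times could be missing. These are more than missing details: followed as written, the analysis gives a diluted or selected comparison.

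**What to change.** Amend Statistical analyses for Objective 2 before outcome data are compared by arm.

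1. **Primary analysis.** Fit one repeated-measures logistic mixed model of delivery and postpartum VL, with arm, visit and arm × visit, and random effects for site and woman. Prespecify one test of the arm effect over both visits, for instance the average of the two visit-specific log odds ratios, and report each visit's effect. Women with one VL then contribute. Other prespecified rules, such as either visit, would also remove the ambiguity but still need a rule for women with one VL.
2. **Weights.** Weight by the inverse probability of having a VL obtained. Use sampling weights if tracing is a sample, and non-response weights if all lost women are pursued; say which applies. Keep the unweighted model as a sensitivity analysis. State how the weights are modelled and scaled, since there are only 12 sites.
3. **Turnaround.** Analyse sample-to-result and result-to-notification separately as time-to-event outcomes with site clustering, censoring results never returned or never notified at end of follow-up. Control-site dates come from paper records, so state how a missing notification date is told apart from an unrecorded one.

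The cost is analysis-plan text, modest programming and somewhat wider intervals from the weights. VL results, dates and tracing status are already within the planned data collection, subject to the control-site caveat above.

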#### ENGAGEMENT WITH HITSYSTEM - INTERVENTION ONLY

49. Since enrolling in ANC, have you received any SMS from the hospital?

- a. No, I have not received any SMS.
- b. Yes, I have received at least one SMS from the hospital but less than 3
- c. Yes, I have received between 3 and 5 SMS
- d. Yes, I have received more than 5 SMS

50. Have you received an SMS for any of the following reasons?

- a. To check how you are doing..... Yes / No
- b. To inform you of your next appointment date..... Yes / No
- c. To remind you to take ART medications..... Yes / No
- d. To let you know your child was due for services..... Yes / No
- e. Asking you to return to the hospital to be informed of a test result..... Yes / No

51. If yes to any option in number 22, please answer question 23 regarding your reaction to receiving the text messages, otherwise skip to 24:
- a. I did not find the SMS helpful.....True / False
  - b. I found the SMS helpful to remember to take medication.....True / False
  - c. I was worried that someone would see the SMS and discover my status .....True / False
  - d. The SMS helped me feel more connected to the hospital/my care provider.....True / False
  - e. The SMS helped me remember when my appointments were.....True / False
  - f. Someone other than me read one of the SMS and asked me about it.....True / False
  - g. A family member or friend discovered my HIV status because of the SMS.....True / False
  - h. The SMS gave me important information regarding my or my infant's care.....True / False
  - i. The SMS motivated me to continue PMTCT and/or EID care.....True / False
52. Please select a preference for frequency of ART adherence messages going forward:
- a. Never, please stop sending me adherence messages
  - b. Daily
  - c. Weekly
  - d. Every two weeks
  - e. Monthly

Thank you for your time and participation.

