#### Engagement with HITSystem 2.1 - **INTERVENTION ONLY**

- 35. Since your child was born, have you received any SMS from the hospital?
  - a. No, I have not received any SMS.
  - b. Yes, I have received at least one SMS from the hospital but less than 3
  - c. Yes, I have received between 3 and 5 SMS
  - d. Yes, I have received more than 5 SMS
- 36. Have you received and SMS for any of the following reasons?
  - a. To check how you are doing.....Yes / No
  - b. To inform you of your next appointment date..... Yes / No
  - c. To remind you to take ART medications..... Yes / No
  - d. To let you know your child was due for services.....Yes / No
  - e. Asking you to return to the hospital to be informed of a test result..... Yes / No
- 37. If yes to any option in number 29, please answer question 30 regarding your reaction to receiving the text messages, otherwise skip to 31.
  - a. I did not find the SMS helpful.....True / False
  - b. I found the SMS helpful to remember to take medication.....True / False
  - c. I was worried that someone would see the SMS and discover my status .....True / False
  - d. The SMS helped me feel more connected to the hospital/my care provider.....True / False

- a. The SMS helped me remember when my appointments were.....True / False
  - b. Someone other than me read one of the SMS and asked me about it.....True / False
  - c. A family member or friend discovered my HIV status because of the SMS.....True / False
  - d. The SMS gave me important information regarding my or my infant's care.....True / False
  - e. The SMS motivated me to continue PMTCT and/or EID care.....True / False
38. Please select a preference for frequency of ART adherence messages going forward:
- a. Never, please stop sending me adherence messages
  - b. Daily
  - c. Weekly
  - d. Every two weeks
  - e. Monthly

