#### Engagement with HITSystem 2.1 - **INTERVENTION ONLY**

- 35. Nyaka ne ichak dhi e ANC, bende iseyudo sms moro a mora ka oa hospital?
  - a. Ooyo,Pok ayudo sms.
  - b. Eeh, Aseyudo achiel, to ma ok ngeny ne adek
  - c. Eeh, aseyudo kind sms 3 kod 5,
  - d. Eeh, Aseyudo sms mohewo
- 36. Bende iseyudo sms moro a moro mapenji wechegi?
  - a. Ngeyo kaka idhi.....Yes / No
  - b. Manyisi chieng ma onego iduogie e hospital..... Yes / No
  - c. Maparoni mondo imwony yath..... Yes / No
  - d. Maparoni mondo iter nyathi e hospital.....Yes / No
  - e. Manyisi mondo idog e hospital mondo inge chal dwako nyathi..... Yes / No
- 37. Kane I yie ne iyudo sms e no 33, kiyie to dwokie penjo no 34 kaka ne itimo bang yudo sms, ka ok kamano to dhie no 35:
  - a. Sms go ne ok okonya.....True / False
  - b. Sms ne okonya mondo apar amwony yath.....True / False
  - c. Ne an kod chandruok ni ngato nyalo neon sms ma ng'e godo chal mara.....True / False
  - d. Sms ne omiya abedo kod e achiel gi hospital/jo thieth.....True / False
  - e. Sms ne omiyo anyalo pare chieng ma onego adogie e hospital.....True / False
  - f. Ng'ato ma opgre koda ne osomo sms ma openja.....True / False
  - g. Ja family kata osiepnna ne ongeyao chal mara nikech sms no.....True / False

- h. Sms ne omiya weche mabeyo kaluwore kod thieth mar nyathina.....True / False
  - i. Sms ne omiya mijingo mondo amend dhi mbele kod yudo thieth mar  
PMTCT/EID.....True / False
38. Kiyie to yier seche ma diher ni mondo waparni godo seche ma onego imwony ART
- a. Okadwar,, kik uorna sms
  - b. Pile
  - c. Juma
  - d. Bang juma 2
  - e. Dwe ka dwe

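### The survey SMS items give only a coarse check of receipt, use a different recall period in the Luo 6-month form, and carry wrong routing numbers in all six forms

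*Combined protocol and SAP*

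**What the plan says.** Under Objective 3, Implementation, fidelity of the SMS component is measured first from the texting logs, by "calculating the proportion of SMS sent according to participant preference (correct frequency and content) and the proportion received by a functioning mobile number". The result is then compared with women's "reports of the number of SMS received as part of the study and the reasons for these SMS". Table 7 lists both the SMS log and the patient surveys as data sources for implementation. The analysis paragraph for Objective 3 says: "Survey data will be summarized using descriptive statistics to calculate proportions, medians, and mean values".

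The survey items are in the intervention-only blocks of the delivery survey (Appendix IIB) and the 6-month survey (Appendix IIC), each in English, Swahili and Luo. Each block has a count item, a reasons item, a reaction item with sub-items, and a preference item (no adherence messages, daily, weekly, two-weekly or monthly). The count item has four answers: none, one or two, three to five, and "Yes, I have received more than 5 SMS". In the English 6-month form its stem is "Since your child was born, have you received any SMS from the hospital". In the Luo 6-month form it is "Nyaka ne ichak dhi e ANC, bende iseyudo sms moro a mora ka oa hospital". The English delivery form introduces the reaction items with "If yes to any option in number 22, please answer question 23 regarding your reaction to receiving the text messages, otherwise skip to 24".

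**The concern.** The survey adds something the logs cannot give. The logs show that a message went out and reached a working number, not that the woman saw it, and item 9 of the enrollment survey allows for shared and borrowed phones. If the items cover different periods by language, or cannot tell six messages from 182, the comparison in the Implementation paragraph is weaker than it appears.

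The reaction block also asks whether a relative or friend learned the woman's HIV status through a message. The confidentiality part of the risk section treats disclosure through message content as a risk to be managed. An interviewer who follows the routing as printed could skip this question for some women and ask it of others.

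**Working it through.** The plan states no figure to reproduce. The check compares the six forms and then works out what the capped count can distinguish.

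**1. Recall period, 6-month form.** English and Swahili ask about the time since the child's birth. The Luo stem is word for word the stem of the Luo delivery form, whose English counterpart asks about the time since enrolling in ANC. One of three language versions therefore covers a longer window. The delivery survey also asks for a new message frequency from then on, so the Luo window can span two chosen schedules. In addition, the top answer in the Luo 6-month form reads "Eeh, Aseyudo sms mohewo" with no number after it in the text as read, whereas the Luo delivery form has the 5. The missing number could be a PDF-reading loss and should be checked on the form itself.

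**2. Routing.** Each routing line names three items: the condition, the question to answer, and the skip target.

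| Form | Items cited | What those items are | Actual reasons / reaction / preference items |
|---|---|---|---|
| English delivery | 22, 23, 24 | partner violence | 50, 51, 52 |
| English 6-month | 29, 30, 31 | COVID-19 (two), first viral load test | 36, 37, 38 |
| Swahili delivery | 34, 36, 37 | COVID-19 | 39, 40, 41 |
| Swahili 6-month | 32, 34, 35 | second and fourth viral load tests, SMS count | 36, 37, 38 |
| Luo delivery | 34, 36, 37 | COVID-19 | 39, 40, 41 |
| Luo 6-month | 33, 34, 35 | third and fourth viral load tests, SMS count | 36, 37, 38 |

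Six of six are wrong. In the Swahili and Luo 6-month forms the skip target lies before the routing line. The English delivery form also jumps from item 33 to item 45, so its own numbering looks like a list error.

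**3. Count cap.** Expected adherence messages = weeks in the window ÷ weeks between messages. The share of schedule at which the top answer is first reached = 6 ÷ expected. Only adherence messages are counted; appointment and other messages would add to the total.

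6-month form, birth to 6 months = 26 weeks:
- daily: 26 × 7 = 182; 6/182 = 3%
- weekly: 26; 6/26 = 23%
- two-weekly: 26/2 = 13; 6/13 = 46%
- monthly: 6; 6/6 = 100%

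Delivery form. The documents do not give the time from ANC enrolment to birth, so 8 to 28 weeks is assumed. Adding 0 to 4 weeks until the survey gives a window of 8 to 32 weeks:
- daily 56 to 224 and weekly 8 to 32, always above 5 if fully delivered
- two-weekly 4 to 16 and monthly about 2 to 7, so full delivery may fall below the top answer

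Luo 6-month form under the same assumption, 8 + 26 = 34 to 28 + 26 = 54 weeks: daily 238 to 378, weekly 34 to 54, two-weekly 17 to 27, monthly about 8 to 12. Every schedule exceeds 5. For monthly messages, six received is then 76% to 48% of schedule, not 100%. The same answer therefore means something different in Luo.

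**4. Planned summaries.** An open top category has no value to average, so this item supports proportions by category but not a mean.

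**The case against.** The strongest reply is that the logs, not the survey, are the fidelity measure. Under-delivery against each woman's chosen frequency is measured whatever she reports. That stands. A reader might infer that SMS fidelity cannot be verified, or that the survey will agree with the logs whatever happened. The documents do not support either reading: a woman logged as receiving weekly messages who answers none, or three to five, is a visible disagreement. The reasons item carries no skip instruction and is half of the planned comparison. For monthly messages in the English and Swahili 6-month forms, one missed adherence message moves the answer down a category unless other messages make it up.

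A reader might also infer that the disclosure answers will be lost. The documents support only a risk. Mentor mothers conduct the surveys on paper, the reaction sub-items are printed directly under the routing line, and study logs separately record adverse events resulting from the study. What remains is that nothing in the forms makes interviewers work around the error in the same way.

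Finally, four of the six intervention sites in Table 2 are in Siaya, so one might conclude that two-thirds of 6-month answers are affected. The documents give no language by site, so no such share can be stated. If Luo is used mainly in Siaya (an assumption), the recall difference would be mixed with region.

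**Conclusion.** The point holds as a set of form errors plus a limit on what one item can show. The Luo 6-month form measures a different period from the other two languages, and its top category needs checking. The routing is wrong in six of six forms, so the reaction items, including SMS-related disclosure, may be skipped or asked inconsistently. Over 26 weeks, the count cannot separate full delivery from receipt of 3% (daily), 23% (weekly) or 46% (two-weekly) of messages. It does detect absent or very low receipt, and the delivery form keeps some discrimination for two-weekly and monthly schedules.

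The percentages rest on adherence messages alone, and the delivery-form and Luo ranges on the assumed 8 to 28 weeks of antenatal follow-up. The items are asked at intervention sites only and are summarized descriptively, so neither primary between-arm comparison is affected. The point is minor in weight, but these are data-collection forms rather than background text, so the errors affect the data collected.

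**What to change.** 1. Change the Luo 6-month stem to ask about the time since the child's birth, and restore the number 5 in its top answer if it is missing on the form.
2. Compare Luo 6-month forms already completed with the texting log from ANC enrolment, and report them separately.
3. Correct the routing so that it names the reasons, reaction and preference items: 36/37/38 in all 6-month forms, 39/40/41 in the Swahili and Luo delivery forms, and 50/51/52 in the English delivery form (or 39/40/41 if its jump from 33 to 45 is renumbered).
4. State under Objective 3 that the survey count is a categorical check of receipt, reported as proportions by answer, with no mean computed from it.

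The count item does not need a new design. A short recent-weeks question, for example, would miss most antenatal messaging at the delivery survey.

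The cost is wording and numbering changes to two surveys in three languages, with no added visits. The sample-size section for Objective 2 describes ten sites still enrolling, so at that stage the corrections can still reach respondents. The downside is that answers collected before and after the correction must be reported separately.
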